Patients eligible to receive TeleGRACE services include:

- Veterans discharged from the Indianapolis VA medical center (VAMC) for an medical/surgical diagnosis (excludes substance use disorder-related admissions; excludes planned admissions)
- Age ≥ 70 years
- Not enrolled in home-based primary care (HBPC)
- Not enrolled in hospice
- Not in dialysis
- Primary care visit within VA in the prior 2 years
- Not residing in nursing home, skilled nursing facility, or CLC
- CAN score $\geq 95^{\text{th}}$ percentile for mortality or missing CAN score
- Discharged from the hospital alive

Exclusion Criteria

- Patients who have been randomized to the control arm after their index hospitalization who become readmitted to the hospital may not be re-randomized.
- Enrolled in in-person GRACE
- Enrolled in home-based primary care (HBPC)
- Enrolled in hospice
- Enrolled in complex care program
- Dialysis (hemodialysis or peritoneal dialysis)
- Residing in nursing home, skilled nursing facility, or CLC
- Living >60 miles from the Indianapolis VAMC facility

Outcome Measures

The primary outcome for the TeleGRACE evaluation will be:

- 90-day all-cause mortality (measured as 90-days from discharge from the index hospital stay)

The secondary outcomes are:

- 90-day readmissions
- 1-year all-cause readmissions
- 1-year mortality
- 1-year ED utilization (VA and non-VA)
- 1-year falls

We will explore using time to nursing home placement as a secondary outcome. We have requested the data and will evaluate the data source for completeness; comparing it against chart review. If the team considers the data source to be accurate, then we will examine time to nursing home placement as a secondary analysis.

Randomization

Patients will be randomized in ratio of 1 (control):2 (intervention) stratified by site of primary care (Indianapolis VAMC versus non-Indianapolis [e.g., CBOCs]). We created a computer-generated randomization list (with random block sizes of 3 or 6) for each strata. With the current capacity

of VA GRACE program staff, our goal is to enroll 5 patients to TeleGRACE each month. The project will seek to enroll a total of 180 patients to TeleGRACE and 360 to usual care in a three-year recruitment period.

Data Sources

Corporate Data Warehouse (CDW) data

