CDW data will be used to assess patient baseline characteristics (e.g., age, demographics, past medical history, prior healthcare utilization) as well as outcomes (i.e., ED utilization, readmission, mortality, and falls). In this way, the same data source is used to identify outcomes for both intervention and control patients.

Chart Review data

Chart review will be used to validate the TeleGRACE dose classification that is based on CDW data (see Per-Protocol analysis described below).

Follow-up Period

Patients will be followed for one year from the date of discharge from their index hospitalization. Unlike clinical trials that require in-person outcome assessments and hence implement “windows” for data collection, this evaluation will use electronic health record data for outcome assessment and hence no windows will be specified.

ANALYSIS PLAN

Intention-to-Treat Analysis

We will compare baseline characteristics between TeleGRACE patients and control patients using chi-square tests for categorical data and t-tests for continuous characteristics.

In the primary intention-to-treat (ITT) analysis, we will compare outcomes between patients randomized to usual care and those to TeleGRACE adjusting for the baseline characteristics that are significantly different by logistic regression for the binary outcome and Poisson regression for count data. If the sample size is sufficient, we will examine the effect of the TeleGRACE program by site of receipt of primary care services.

Per-Protocol Analyses

Not all patients who are randomized to receive TeleGRACE will receive services from the TeleGRACE staff. This situation is anticipated for patients who decline GRACE and others who become ineligible after discharge from the index hospitalization but before their first virtual home visit post-discharge (e.g., patients who die, get readmitted, or move to a skilled nursing facility after discharge). In the exceptionally rare case, patients may be discharged from TeleGRACE due to safety concerns for our staff (e.g., sexually or physically aggressive behavior, unwillingness to cage animals, unwillingness to store firearms). The per-protocol analyses will be similar to the planned intention-to-treat analysis but will compare the outcomes between patients who received GRACE service versus patients in usual care.

Given the expected heterogeneity in the number of TeleGRACE visits, patients will be classified into four categories as follows:

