1. **Full TeleGRACE dose:** the patient received a virtual post-discharge transitional visit, followed by a virtual baseline visit with multidisciplinary team discussion, and then follow-up virtual discussion to ensure that the patient and caregiver agree with and understand the plan of care. These patients may receive additional follow-up contacts with the TeleGRACE/GRACE team members over the course of the one year follow-up period. Note: in the atypical situation where the patient did not receive a transitional visit but did receive a baseline assessment, the patient will still be classified as "full TeleGRACE dose").
2. **Transitional visit dose:** the patient received a virtual post-discharge transitional visit but did not receive a baseline visit. These patients may receive additional follow-up contacts (typically by telephone) with the TeleGRACE/GRACE team members over the course of the one-year follow-up period. In some cases, the patient may receive multiple transitional visits (e.g., after readmissions).
3. **Partial dose:** the patient received neither a post-discharge transitional visit nor a baseline visit but had other contact with the TeleGRACE/GRACE team (typically telephone visits).
4. **No TeleGRACE:** patients may have been contacted by the TeleGRACE/GRACE team in an attempt to schedule a visit, but these patients received no clinical visits or encounters. Patients who decline TeleGRACE services are included in this category. Please note: in a research randomized controlled trial, only patients who are potentially interested in participation are consented and then randomized. TeleGRACE is a quality improvement project, therefore enrollment follows procedures used in clinical care.

We will further examine the outcomes among patients across these 4 categories as well as the control patients.

Sensitivity Analyses

Considering the heterogeneity in the TeleGRACE patients, we plan to conduct the following sensitivity analyses

1. **Enrolled versus Randomized to TeleGRACE:** We will conduct the ITT analysis described above which compares patients *randomized* to TeleGRACE versus usual care controls. In addition, we will compare patients who *enrolled* in TeleGRACE versus control patients.
2. **Dose:** In addition to the description of TeleGRACE services as provided in the per-protocol analysis, the dose of the TeleGRACE program will be assessed in terms of:

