 - a. The total number of GRACE contacts (telephone, virtual or in-person) in the one-year post-discharge from the index event.
 - b. Typically, home visits are conducted by a dyad of a nurse practitioner and social worker. Given staffing constraints, some patients may only receive a visit by a social worker or a nurse practitioner but not both. Therefore, each transitional, baseline, and follow-up visit will be assessed to describe whether it was conducted by social work, nursing, or other staff.
 - c. A key element of the GRACE program is the development of a multidisciplinary plan via discussion at the weekly GRACE rounds. The number of times an individual patient is discussed by the entire team in the year post-discharge will

be recorded (the geriatrician's summary of the multidisciplinary discussion will be used to identify whether a patient was discussed during team rounds).

3. **Discontinuous Eligibility Periods:** Patients who become permanently ineligible for TeleGRACE (e.g., are readmitted and then subsequently discharged to a long-term care facility) will be censored on the date they became ineligible for the outcome measures because they became ineligible for services. However, this censoring plan will be implemented retrospectively because it is expected that the older persons who will be enrolled in this study may have intermittent periods of ineligibility (e.g., during a hospital stay and then followed by short-term rehabilitation stay). Such patients may still benefit from the intervention and hence will not be censored either from the intervention or control groups.
 - a. For all intervention patients, we will calculate the proportion of eligible days a patient is cared for by the GRACE team as: the number of days that the patient was under the care of the GRACE team divided by the total number of days the patient was potentially eligible for GRACE.
 - b. We will note whether the period of eligibility was either continuous or discontinuous.
 - c. For patients with a discontinuous eligibility period, we will describe the patterns of discontinuity. For example, some patients may have a short hospital stay early post-discharge but then receive a relatively long period of GRACE services in the year post-discharge. In contrast, other patients may have recurrent hospitalizations some of which may be followed by short-term rehab stays resulting in fragmented eligibility periods of relatively short durations.

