 - d. If there are more than 10% patients censored for the outcomes, we will conduct Cox-regression analysis for the hazard of death and risk-exposure adjusted Poisson regression for the number of readmissions and number of falls.

POWER

For **Aim 1** (effectiveness of TeleGRACE versus usual care), we expect to observe 2% and 8% 90-day all-cause mortality for the TeleGRACE and usual care patients, respectively. This projected effect size is conservative based on our propensity-score weighting analysis comparing GRACE patients with usual care patients. With 180 TeleGRACE and 360 usual care patients, the study has 0.96 power at detect the efficacy of TeleGRACE program with a one-sided normal test at a significance level 0.05. Considering a 10% drop-out, the analysis has 0.94 power to establish the TeleGRACE efficacy with the same effect size.

DATA MONITORING

Enrollment

We will closely monitor the randomization of TeleGRACE with the expected rate of 5 per month. We will plot the number of actual randomized patients and its expected number against the study time and update the figure on a monthly basis. Prior to the DSMB meeting, we will estimate the current randomization rate and project the final number of randomized patients by end of the fourth year with the current rate along with its 95% confidence interval based on the Poisson distribution. If the upper bound of the 95% interval is below the target number of 180. We will modify the enrollment strategy to ensure that we achieve the enrollment goal.

Interim Analysis

Since the observed effect size of in-person GRACE versus usual care is quite substantial with respect to 90-day all-cause mortality, we plan an interim analysis when a half of the enrolled patients can be evaluated for the primary outcome. One-sided normal testing will be applied for the interim analysis using O'Brien-Fleming group sequential test with the overall type error controlled at 0.05. The hypotheses are:

$$H_0: p_1 = p_2 \text{ vs. } H_1: p_1 < p_2,$$

where p_1 and p_2 stand for the 90-day all-cause mortality in TeleGRACE and usual care arms, respectively.

If the Z – test statistic crosses the boundary of -2.54 at the interim analysis, the trial will be recommended for stopping for efficacy; otherwise, the trial will continue to the end with the crossing boundary for the test statistic at -1.66. The overall power with the interim analysis for this study is 0.82.

Safety

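### Count secondary outcomes are specified only as Poisson regression with no robust variance or dispersion term, so intervals will be too narrow if the counts are overdispersed

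*Combined protocol and SAP*

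**What the plan says.** The Intention-to-Treat Analysis section assigns logistic regression to the binary outcome and "Poisson regression for count data", in each case "adjusting for the baseline characteristics that are significantly different" between the arms. It names no variance estimator, dispersion check or exposure term.

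The Per-Protocol Analyses section carries this over: "The per-protocol analyses will be similar to the planned intention-to-treat analysis". It then compares four TeleGRACE dose categories and the controls.

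The Outcome Measures section lists readmissions at 90 days and one year, one-year falls and one-year ED utilization, without saying which are counts. Sensitivity Analyses item 3d does treat two of them as counts. It applies only under a condition, "If there are more than 10% patients censored for the outcomes", and then calls for "risk-exposure adjusted Poisson regression for the number of readmissions and number of falls". ED utilization is not named there.

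Item 3c expects patients to differ in their course. Some have one short early hospital stay, whereas "other patients may have recurrent hospitalizations some of which may be followed by short-term rehab stays".

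**The concern.** Ordinary Poisson standard errors assume that, given the covariates, the variance of the count equals its mean. If some patients are repeatedly readmitted or fall often while most are not, the variance exceeds the mean and those standard errors are too small. A chance difference in readmissions or falls, in either direction, could then be reported as an effect of TeleGRACE.

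Two features of the plan might seem to protect against this.

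- **Covariate adjustment.** A covariate enters only if it differs significantly between arms. In a randomized comparison that selects on chance imbalance, not on prognostic strength. Prior utilization, which the plan collects, would enter about 5% of the time if the baseline tests use 0.05 (an assumption; no level is stated).
- **Item 3d.** It is a conditional sensitivity analysis, it is still Poisson, and it omits ED use. An exposure offset accounts for time at risk, not for patients having different underlying rates.

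**Working it through.** **The plan's own figures.** None is given for any count outcome: no rate, dispersion, power, alpha or sidedness. The one stated power is for 90-day mortality (2% vs 8%, 180 TeleGRACE and 360 usual care, one-sided 0.05). It reproduces with unpooled variance: SE = √(0.02×0.98/180 + 0.08×0.92/360) = 0.0177; 0.06/0.0177 − 1.645 = 1.745; Φ(1.745) = 0.96. This point does not touch it.

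**Inputs.** Arm sizes are 180/360 as in the Randomization and Power sections. 360/180 was also run, because the Randomization section separately states 1 control to 2 intervention. Assumed, because the documents give no value: mean count μ of 0.3 to 2.0 per patient and negative-binomial dispersion k of 0 to 1.0.

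**Formula.** Variance/mean is d = 1 + μk. The correct standard error is √d times the Poisson one. With no true effect, a nominal two-sided 5% test rejects with probability 2Φ(−1.96/√d), and a one-sided 0.05 test for benefit with probability Φ(−1.645/√d). Coverage of the 95% interval is one minus the two-sided figure.

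| μ | k | d | Two-sided | One-sided | Coverage |
|---|---|---|---|---|---|
| any | 0 | 1.00 | 5.0% | 5.0% | 95.0% |
| 0.3 | 0.1 | 1.03 | 5.3% | 5.3% | 94.7% |
| 2 | 0.1 | 1.20 | 7.4% | 6.7% | 92.6% |
| 0.3 | 0.5 | 1.15 | 6.8% | 6.3% | 93.2% |
| 0.3 | 1 | 1.30 | 8.6% | 7.5% | 91.4% |
| 1 | 1 | 2.00 | 16.6% | 12.2% | 83.4% |
| 2 | 1 | 3.00 | 25.8% | 17.1% | 74.2% |

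**Simulation, no true effect, k 0.5 to 1.0.** Plain Poisson rejects (two-sided) in 6.6 to 25.4% of trials at 180/360 and 6.5 to 26.3% at 360/180. The robust/plain SE ratio is 1.07 to 1.72. At k = 0 the ratio is 0.997.

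**Does adjustment cure it?** Suppose a prognostic covariate were always included, which is better than the plan guarantees. Two-sided rejection is then still about 6 to 23% if it explains 25% of the log-rate variance, and about 5 to 18% if it explains 50%.

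**Does an offset cure it?** Holding the plan's 2% and 8% 90-day mortality constant over a year (an assumption) gives follow-up loss of 1 − 0.98^(365/90) = 7.9% and 1 − 0.92^(365/90) = 28.7%. With equal event rates and a log-time offset, plain Poisson rejects in about 7 to 25%. Item 3 defines censoring by permanent ineligibility rather than death, so this only illustrates that an offset leaves overdispersion in place.

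**Robust standard errors.** With full arms and equal follow-up or an offset, rejection is about 4.6 to 6.2%. A second simulation with 2,000 trials per cell, which also covered 180/90, gave robust coverage of 93.0 to 95.9%. Its Monte Carlo standard error is √(0.05×0.95/2000) ≈ 0.5 percentage points.

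**Where robust errors fall short.**

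- *Small categories.* Against 360 controls with k = 1 and μ of 1 to 2 (category sizes assumed), sandwich errors reject in about 9 to 11% at 10 patients, about 8% at 20 and about 7% at 30.
- *Unequal follow-up without an offset.* Under the loss above, with equal event rates, robust Poisson on total counts rejects in about 10 to 18%.

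**The case against.** The strongest reply is that the SAP is silent on the variance rather than wrong about it. It names no estimator for logistic regression either, and an analyst might add robust errors unprompted. That stands as far as it goes: a reader might infer that the plan has ruled robust errors out, and it has not. But unqualified Poisson regression ordinarily means model-based errors. Leaving the choice open until results are known is itself a weakness.

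Second, the documents do not show overdispersion. Recurrent hospitalizations in some patients also occur under a pure Poisson model: with mean 1, 1 − 2e⁻¹ = 26% of patients have two or more events; with mean 0.3, 1 − 1.3e⁻⁰·³ = 4%. Entry is also restricted to patients aged 70 or over with a recent discharge and a mortality risk score at or above the 95th percentile, or missing, which may narrow the spread of risk. This stands. Overdispersion is plausible here, not documented.

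Third, which outcomes are counts is not fully settled. Item 3d supports readmissions and falls, but 90-day readmission could be analysed as binary and ED use is unclassified. This limits the scope without removing the point.

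Fourth, negative binomial regression would serve as well. That is right; preferring the sandwich is a matter of convenience.

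**Conclusion.** The point holds conditionally. As written, the plan gives intervals that are too narrow for any count outcome that proves overdispersed, and its other provisions do not reliably prevent this. Under assumed means of 0.3 to 2.0 and dispersion of 0.5 to 1.0, a two-sided 5% test rejects in about 6 to 26% of null trials, and 95% intervals cover about 74 to 93%. With little or no dispersion the problem is slight or absent.

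A reader might infer that a quarter of null comparisons will come out significant. That figure needs mean 2 and dispersion 1, and nothing in the documents establishes either. A reader might also infer that the trial's main conclusion is at risk. It is not: only secondary outcomes are affected, and the point estimates, 90-day mortality, the stated power and the interim analysis are untouched. This is an inexpensive improvement worth making before analysis.

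**What to change.** In the Intention-to-Treat Analysis section, replace "Poisson regression for count data" with *Poisson regression with robust (sandwich) standard errors for count data*. Use the same variance in the overall per-protocol comparison and in Sensitivity Analyses item 3d. Negative binomial regression is an acceptable alternative if it is pre-specified.

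Two limits should be written in alongside:

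- For dose categories of roughly 10 to 30 patients, use a small-sample correction or report the comparison descriptively.
- Robust errors do not correct for unequal follow-up in a model without an offset, so the SAP should not rely on them for that.

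The change needs no new data. Under the assumed range, intervals become about 7 to 72% wider on the log scale, so some nominally significant secondary results would no longer be so. If there is no overdispersion, intervals are essentially unchanged.

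### The per-protocol mortality comparison drops TeleGRACE patients who die before any service but keeps every usual-care death, so it is biased by survival and selection

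*Combined protocol and SAP*

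**What the plan says.** - **Outcome** (METHODS, Outcome Measures): the primary outcome is "90-day all-cause mortality (measured as 90-days from discharge from the index hospital stay". The clock starts at discharge in both arms.
- **Comparison groups** (ANALYSIS PLAN, Per-Protocol Analyses): the analysis "will compare the outcomes between patients who received GRACE service versus patients in usual care". No matching restriction is placed on usual-care patients.
- **Reasons for no service** (same section): patients may decline, or may become ineligible "before their first virtual home visit post-discharge (e.g., patients who die, get readmitted, or move to a skilled nursing facility after discharge").
- **Model**: similar to the ITT analysis, that is, "adjusting for the baseline characteristics that are significantly different by logistic regression for the binary outcome".
- **Dose categories**: the plan sets out four. Category 3 (partial dose) had neither a transitional nor a baseline visit but "had other contact with the TeleGRACE/GRACE team (typically telephone visits"). For category 2, "the patient may receive multiple transitional visits (e.g., after readmissions"). For category 4 (no TeleGRACE), "Patients who decline TeleGRACE services are included in this category". The plan adds: "We will further examine the outcomes among patients across these 4 categories as well as the control patients".
- **Enrolled contrast** (Sensitivity Analyses, item 1): enrolled TeleGRACE patients are also compared with controls. Enrolled is not defined.

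**The concern.** Membership of the TeleGRACE side of this comparison depends on something that happens after time zero: surviving, and staying reachable and eligible, until service is delivered. Membership of the usual-care side does not. Time from discharge to first service is therefore death-free by construction in one arm only (immortal time).

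Three further selections may act on the same contrast. Decliners fall out. So may patients readmitted or placed in a facility before service, although category 2 shows that some readmitted patients are still visited later. Whether a telephone-only patient counts as served is not stated; if so, the immortal interval is shorter but does not vanish.

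The four dose categories keep everyone, but early deaths collect in the lower ones, so a dose gradient can arise from survival alone. The enrolled contrast shares the fault only if enrolment requires contact or acceptance after discharge.

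At stake is interpretation. The hypothesis is worded in terms of patients who receive TeleGRACE, so readers may take the received-service result as direct evidence for or against the program.

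**Working it through.** **1. Inputs from the plan.** POWER gives 8% usual-care mortality, 180 TeleGRACE and 360 usual-care patients, and a one-sided 0.05 test. No figure is given for the per-protocol analysis. The stated ITT power reproduces with an unpooled one-sided normal test: Φ(0.06/√(0.02×0.98/180 + 0.08×0.92/360) − 1.645) = 0.9595 (stated 0.96), and 0.9419 with 162 and 324 (stated 0.94). The Randomization section gives 1 control to 2 intervention, which conflicts with 180 and 360, so both orientations are shown.

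**2. Assumptions, not in the plan.** No true effect; constant hazard; every TeleGRACE survivor first served on day t; one-sided 0.05 carried over to this analysis.

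**3. Direction.** Let f be the share of 90-day TeleGRACE deaths that occur before service. Recipient mortality is p(1 − f)/(1 − pf). The recipient odds are p(1 − f)/(1 − p), so under no effect the odds ratio equals 1 − f. Dropping early deaths alone always favours TeleGRACE.

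**4. Size.** F(t) = 1 − 0.92^(t/90); recipient mortality p₁ = (0.08 − F(t))/(1 − F(t)). For t = 14: F = 0.0129, so p₁ = 0.0671/0.9871 = 0.0680. The rejection rates are exact binomial enumerations of an unadjusted log-odds Wald test, the closest simple form of the planned logistic model. The number of TeleGRACE recipients is the arm size times 1 − F(t), rounded.

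| First service | Recipient mortality | Risk ratio | Rejection, 180 v 360 | Rejection, 360 v 180 |
|---|---|---|---|---|
| no bias | 8.0% | 1.00 | 4.4% | 5.1% |
| day 3 | 7.7% | 0.97 | 5.4% | 6.4% |
| day 7 | 7.4% | 0.93 | 7.3% | 8.5% |
| day 14 | 6.8% | 0.85 | 11.3% | 12.8% |
| day 30 | 5.4% | 0.68 | 27.1% | 32.5% |

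(TeleGRACE is listed first in each pair.)

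**5. Decliners.** Assume 30% decline, with r times the accepters' mortality. Accepters' mortality is m = 0.08/(0.7 + 0.3r), and recipients are at 1 − (1 − m)^((90 − t)/90). Results are for 180 v 360.

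| r | m | Recipients at day 7 / 14 / 30 | Rejection at day 7 / 14 / 30 |
|---|---|---|---|
| 0.5 | 9.4% | 8.7% / 8.0% / 6.4% | 2.5% / 4.1% / 12.1% |
| 1.5 | 7.0% | 6.4% / 5.9% / 4.7% | 11.8% / 16.2% / 30.3% |

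Lower-risk decliners can cancel or reverse the bias; higher-risk decliners enlarge it.

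**6. Dose categories.** If the baseline visit falls on day 30 (assumed), 180 × F(30) = 4.9 of 180 × 0.08 = 14.4 expected TeleGRACE deaths fall below full dose. Full dose then shows 5.4% mortality with no program effect.

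**7. Does a complier-average estimate do better?** In 200,000 simulated trials (180 v 360, 30% declining at equal risk, hazard halved from service at day 14), the true effect in those served was −0.0334. The complier estimate averaged −0.0333, the received-service contrast −0.0454 and ITT −0.0231.

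**The case against.** - **It is a supportive analysis.** ITT is primary, and neither the power statement nor the stopping boundary uses the per-protocol contrast. This stands; the point does not threaten the trial's main conclusion.
- **The one-sided level is borrowed.** The plan attaches it to the power statement and the interim test and gives no sidedness for the per-protocol models. With a two-sided 0.05 test, the rates of a false finding favouring TeleGRACE (180 v 360) are 2.5%, 3.4%, 5.7% and 16.1% at days 3, 7, 14 and 30, against 2.0% with no bias. The absolute rates are roughly half; the relative inflation is similar.
- **The largest figures need late first service.** A transitional visit precedes the baseline visit, and telephone contact may count as service, so day 30 for first contact is an extreme case. If contact comes within a week, the inflation from early deaths is small. The plan gives no service day, so late service cannot be excluded.
- **The net direction is uncertain.** This is correct once decliners are included. An unknown sign makes the contrast harder to interpret, not safer.
- **The deaths will be visible**, because the no-TeleGRACE category is reported. That discloses the problem without correcting the contrast.
- **The remedies have faults.** The complier estimate needs strong assumptions, and a landmark keeps some selection. Both limits are real and must be stated alongside the results.

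The censoring and Cox step in Sensitivity Analyses, item 3, does not answer the concern. It deals with permanent ineligibility, not survival to first service.

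**Conclusion.** The concern holds. Followed as written, the per-protocol rule conditions on survival to service in the TeleGRACE arm only, and nothing in the plan corrects it. The fault follows from the text; its size does not. Under the assumptions in steps 2 and 4, the spurious risk ratio from early deaths alone is about 0.93 to 0.85 for first service at day 7 to 14, closer to 1 for earlier contact and 0.68 at day 30. Selection by declining, readmission or facility placement can move the result either way by an amount the documents do not allow one to calculate. The primary ITT analysis is not affected. This should be corrected before analysis.

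**What to change.** 1. State that the mortality conclusion rests on ITT.
2. Define received service, assessed by the outcome's cut-off day, and define enrolled.
3. Replace the received-service contrast with a complier-average estimate: the ITT risk difference divided by the proportion of the TeleGRACE arm that received service. Do the same for the enrolled contrast if enrolment depends on post-discharge contact. Count any clinical contact, including telephone-only partial dose, as service. State the assumptions: assignment affects mortality only through that service, and usual-care patients receive none of it. Because the planned model is logistic, say how the risk difference will be obtained.
4. Alternatively, use a landmark: restrict both arms to patients alive at a fixed day, classify service only by contacts up to that day, and count mortality from then. Label it as not removing selection by declining, readmission or facility placement before service.
5. Report outcomes by dose category descriptively, without causal dose-response claims. Labelling the received-service contrast non-causal is the least that should be done, but that leaves its bias in place.

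**Cost.** SAP wording and modest programming.

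- *Complier estimate:* the interval is wider. The ITT standard error is √(0.08×0.92/180 + 0.08×0.92/360) = 0.025; with 30% declining, the complier value is about 0.036 by simulation. It is biased if uncounted contact matters: in the step 7 setting, with 20% of accepters telephone-only, equally helped and not counted as served, it averaged −0.0416 against a true −0.0334.
- *Landmark:* it loses F(7)/0.08 = 8% of 90-day deaths at day 7, or F(14)/0.08 = 16% at day 14. It also keeps some selection. If 10% are unserved through readmission or placement and have twice the others' mortality (assumed), the others' 90-day mortality is 0.08/(0.9 + 0.1×2) = 7.27%. From day 7, served patients are then at 6.73% against 7.40% in controls, a risk ratio of 0.91 with no true effect.
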